### **6.7 Concomitant Medications**

Version 4.0 Date: 08/21/2020

NCT02463799

The values for radium-223 in this protocol has been revised as per the US NIST standardization update (agreed on 17 Mar 2015)

The subject's current prescription and nonprescription medications will be reviewed at the screening visit and recorded in the subject's medical record and on the CRF. Medications taken from registration through the week 20 will also be recorded. Any medications associated with a possible or probable treatment-related AE will be recorded on the CRF, regardless of when they are taken. The concomitant medication administered, indication, dose, route, frequency, and start and stop dates will be recorded in the subject's medical record and on the CRF.

### **6.7.1 Anticancer Therapies**

All anticancer therapies received prior to screening and through the end of the follow-up will be recorded in the subject's medical record and on the CRF. Anticancer therapies include, but are not limited to, radiation, chemotherapy, hormone therapy, investigational cancer therapies, all other systemic therapies, and surgery. The start/stop date and dose of anticancer therapies will be recorded.

### **6.7.2 First Cancer-Related Opioid Use**

Each subject's first cancer-related opioid use, as determined by the investigator, will be recorded in the subject's medical record and on the CRF. Cancer-related opioid use is defined as use for cancer-related pain that is of at least 2 consecutive days in duration.

Opioid analgesic use for treatment or prevention of infusion reactions, such as chills or rigors, post-procedural pain, or for indications clearly unrelated to cancer pain (e.g., cough, pain due to an injury or accident) should NOT be considered cancer related.

## **6.8 Survival Status**

Confirmation of survival status will be obtained by speaking directly with the subject on the telephone or in person. Death certificates will be obtained as a source document for the date and cause of death recorded on the CRF.

If a death certificate cannot be obtained, one or more of the following documents (in preferential order) will be the source document for the date and cause of death:

1. SSDI/NDI (date of death only).
2. Hospital report.
3. Hospice report.
4. Clinical chart note.
5. Other medical records.

## **6.9 Laboratory Test Assessments**

Version 4.0 Date: 08/21/2020

NCT02463799

The values for radium-223 in this protocol has been revised as per the US NIST standardization update (agreed on 17 Mar 2015)

At the times noted in Table 1, blood samples will be obtained for assessment of the parameters presented in Table 2.

Table 2: Clinical Laboratory Tests

Hematology	Chemistry
hemoglobin	sodium
hematocrit	potassium
platelets	bicarbonate
mean corpuscular volume	chloride
mean corpuscular hemoglobin	lactate dehydrogenase
mean corpuscular hemoglobin concentration	blood urea nitrogen
leukocytes	creatinine
neutrophils	phosphorus
lymphocytes	calcium
monocytes	magnesium
eosinophils	glucose
basophils	albumin
	total protein
	total bilirubin
	alkaline phosphatase
	alanine aminotransferase
	aspartate aminotransferase
Other Assessments	
total testosterone	
prostatic specific antigen	
Coagulation	
prothrombin time	
Partial thromboplastin time	
international normalized ratio	

## 6.10 Immune Assessments

### 6.10.1 Peripheral Immune Response Assessments

Cellular and humoral immune responses will be assessed from 100 mL blood samples (9x10 mL heparin whole blood tubes and 1x10 mL serum tube) collected at the times noted in the Schedule of Assessments (Table 1).

Immune response assessments will include T-cell activation to PA2024 and PAP using IFN- $\gamma$  ELISPOT assay, T-cell proliferation response to PA2024 and PAP by  $^3\text{H}$ -thymidine uptake, and humoral (IgG and IgM) response to PA2024 and PAP by ELISA.

Version 4.0 Date: 08/21/2020

NCT02463799

The values for radium-223 in this protocol has been revised as per the US NIST standardization update (agreed on 17 Mar 2015)

The following research blood samples should be collected and processed as instructed in Immune Monitoring Requisition Form (Appendix 1):

Ship the specimen as instructed in Immune Monitoring Shipping Instructions (Appendix 2)

### **6.10.2 Antigen Spread Assessment**

Antigen spread induced by sipuleucel-T treatment will be evaluated by measuring humoral (IgG) response to 10 off-target antigens which were previously identified from subjects in the sipuleucel-T arm of IMPACT study using protein microarrays (ProtoArrays) [17]. Serum IgG level against each antigen will be measured using Luminex xMAP.

Exploration of new secondary antigens will also be performed by detecting significant IgG responses using the protein microarray.

At each time points (baseline, 1st pre-leukapheresis visit (only in Arm 1), and weeks 14 and 52 post-first sipuleucel-T infusion), the following research blood samples should be collected and processed as outlined below:

- Draw approximately 10 mL of peripheral blood into 2 plain (red top) or SST (gold top) tubes, each containing  $\geq 5$  mL of blood per vacutainer.
- Allow blood to coagulate for 20 minutes, then centrifuge at 25C, 1500 x g (2700-3000 rpm), for 15 minutes.
- Pipette the serum into 10 cryotubes (about 0.5 mL/tubs).
- Store cryotubes frozen, at - 80 C , until the time of analysis

**Antigen Spread analysis** will be performed in the Laboratory of [name] MD/PhD at Johns Hopkins. Plasma pharmacokinetic samples collected at outside institutions should be shipped on dry ice (a minimum of 5 kg) to laboratory at Johns Hopkins, at the address below. Overnight shipments should occur on Monday–Thursday, except when the following day is a holiday. A fax or call should be placed to the laboratory prior to shipment, providing the tracking information.

### **6.10.3 Product Immune Parameter Assessments**

Prior to infusion, small samples (3% to 4%) of cellular components from pre and post-culture (PA2024) cells will be used to assess product potency as part of the normal sipuleucel-T manufacturing process. The data of the product immune parameters will be obtained for analysis for correlation with clinical outcome.

### **6.11 Study Materials**

The clinical trial site will have a calibrated scale for recording body weight and a calibrated sphygmomanometer and thermometer for vital signs assessments. A current and fully stocked advanced cardiac life support cart will be immediately available on the premises. The clinical trial site will also have a refrigerated centrifuge, a monitored and alarmed refrigerator, and a freezer (-20°C or below) as well as containers and dry ice for shipment of blood samples.

The clinical trial site will provide all materials required for accurate documentation of subject visits and study activities.

Materials needed for the collection of laboratory samples, including immune monitoring samples, will be provided by Dendreon.

## **7.0 ADVERSE EVENTS**

An AE is defined as any untoward medical occurrence in a subject while on study that does not necessarily have a causal relationship with the treatment. An AE can, therefore, be any unfavorable and unintended sign (e.g., abnormal laboratory finding), symptom, or disease temporally associated with the treatment, whether or not considered related to the treatment. Adverse events include exacerbation of a pre-existing illness, an increase in frequency or intensity of a pre-existing episodic event or condition, a condition detected or diagnosed after product administration (even though it may have been present prior to the start of the study) or a continuous persistent disease or symptoms present at screening that worsen following the start of the study.

### **7.1 Categories for Ranking Severity of Adverse Events**

The NCI CTCAE [2] will be used to score AE severity. In general, the following general severity definitions apply:

Version 4.0 Date: 08/21/2020

NCT02463799

The values for radium-223 in this protocol has been revised as per the US NIST standardization update (agreed on 17 Mar 2015)

Mild (Grade 1):	The AE results in mild, easily tolerated symptoms, or is asymptomatic with clinical or diagnostic observations only. Intervention is not usually indicated.
Moderate (Grade 2):	The AE produces moderate symptoms with discomfort sufficient to interfere with some aspect of the subject's normal daily activity. Minimal, local, or noninvasive intervention is required.
Severe (Grade 3):	The AE is medically significant but not immediately life threatening, results in discomfort or disability which is incapacitating and prevents most normal daily activities, clearly damaging to the health, requiring hospitalization, prolongation of existing hospitalization or complicated treatment.
Life Threatening (Grade 4):	The AE could reasonably result in death unless immediate medical intervention is undertaken.
Fatal (Grade 5):	The AE results in death.

## 7.2 Relationship of Adverse Events to Study Treatments

The following categories will be used to determine relatedness of AEs to study treatments:

None:	The AE is clearly related to other factors, such as the subject's clinical state, environmental factors, or other modes of therapy or concomitant medications administered to the subject.
Possible:	The AE follows a reasonable temporal sequence from administration of study treatment, but could readily have been produced by the subject's clinical state, environmental factors, or other modes of therapy or concomitant medications administered to the subject.
Probable:	The AE follows a reasonable temporal sequence from administration of study treatment and cannot readily have been produced by the subject's clinical state, environmental factors, or other modes of therapy or concomitant medications administered to the subject.

## 7.3 Adverse Events Reporting

The principal investigator will notify the appropriate regulatory agencies of any SAEs occurring during the study period, regardless of causality. These agencies include the Sidney Kimmel Comprehensive Cancer Center (SKCCC) Data and Safety Monitoring Committee (DSMC), and the Institutional Review Board (IRB) and the Institutional Biosafety Committee (IBC) of the Johns Hopkins Medical Institutions (JHMI). The representatives of Dendreon will also be notified. Expedited reporting to the PI within 24 hours is required for all SAEs (see Section 7.4.1). For SAEs that are fatal, life-threatening, or treatment-related but non-life threatening: IRB/IBC reporting by the PI is required within 3 days. For unrelated SAEs, IRB/IBC reporting

by the PI is required within 15 days. All other AEs should be documented on CRFs and submitted according to the standard data management guidelines.

Adverse event information will be collected continuously throughout the duration of the study. Participants will be instructed to notify their treating provider of any new signs or symptoms, and providers will actively assess patients for adverse events at each visit (including by evaluation of laboratory studies). The investigator will assess each AE for its severity and for its relationship to the study drug, and all events Grade 1 or higher will be documented on CRFs and then reported as described above within the required time frame. Any AE occurring while a patient is on study (*i.e.* after informed consent has been signed) or within 30 days of study termination requires reporting. AEs occurring later than this must still be reported if a causal relationship with the study drug is suspected.

For all AEs, the investigator must pursue and obtain information to adequately determine the causality and outcome of the event, and to assess whether it meets criteria for a SAE. In addition, follow-up of an AE is required until the event either resolves or stabilizes.

The principal investigator must keep copies of all CRFs and other AE information, including correspondence with the IRB and/or FDA, for as long as required to comply with national and international regulations.

## **7.4 Serious Adverse Events**

An SAE is defined as any adverse drug experience occurring at any dose that results in any of the following outcomes: death, a life threatening adverse drug experience, subject hospitalization or prolongation of an existing hospitalization, a persistent or significant disability/incapacity, or a congenital anomaly/birth defect. An important medical event that may not result in death, be life threatening, or require hospitalization may be considered a SAE when, based upon appropriate medical judgment, it may jeopardize the subject and may require medical or surgical intervention to prevent one of the outcomes listed in this definition. Examples of such medical events include allergic bronchospasm requiring intensive treatment in an emergency room or at home, blood dyscrasias or convulsions that do not result in subject hospitalization, or the development of drug dependency or drug abuse.

### **7.4.1 Serious Adverse Event Collection and Reporting**

All SAEs and unknown/unexpected reactions that occur from the signing of the study-specific consent through the duration of the post-therapy adverse event collection should be reported to the Study Coordinator, Dendreon Safety Manager, and Bayer Global Pharmacovigilance within 24 hours of being made aware of the SAE. If the Study Coordinator cannot be reached within 24

hours, the PI ([name] MD) should be contacted at [contact] or at [[contact]](mailto:[contact]). Notification can be made via phone or telefacsimile or email.

#### Bayer

Attn: Global Pharmacovigilance - USA  
Email: [[contact]](mailto:[contact])  
[contact]  
Address:  
Mail only: Bayer HealthCare  
[name]  
Address: [name]  
FDX or UPS only [name] for UPS

Reports for all Bayer products can also be phoned in via our Clinical Communications Dept:  
[contact]

The initial report for each SAE or death to the Study Coordinator should include the following information:

- name and contact information of the reporter
- protocol # and title
- patient identified by one or more of the following:
  - patient initial
  - patient identification number
  - knowledge that a patient who experienced the adverse event exists
  - age
  - sex
- date the event occurred
- description of the SAE

Version 4.0 Date: 08/21/2020

NCT02463799

The values for radium-223 in this protocol has been revised as per the US NIST standardization update (agreed on 17 Mar 2015)

- investigational agent(s) received (and dose level) at the time the SAE occurred
- time from administration of the investigational agent(s) to start of the event
- description of the patient's condition

Follow-up information including severity, causality, action taken, concomitant medications, and outcome should be communicated to the principal investigator as soon as possible with an indication whether an amendment will need to be made to the protocol, the consent form, or both, as a result of this event.

The Investigator may report serious adverse drug reactions (SADRs) using either:

An ADEERS form (Adverse Event Expedited Reporting System) available at <http://ctep.cancer.gov/reporting/adeers.html>

OR

A MedWatch form available at <http://www.fda.gov/medwatch/>

The report of SAE to Dendreon should be made using an SAE Report Form provided by Dendreon (Appendix 3). Significant new information regarding an ongoing SAE and the resolution must be sent to Dendreon within 3 business days of awareness of the new information to Dendreon on the SAE Report Form.

Sponsor investigator shall notify institution, co-investigators and IRB immediately during the conduct of the study and/or after the study is completed should it become aware of information related to the study that would impact participant safety or clinical care. Institution shall promptly disclose such information to study participants.

## **7.5 Death Reports**

Death is an expected outcome of this study. Deaths that meet any of the following criteria must be reported as an SAE:

- Deaths that occur within 30 days of receiving the last study treatment.
- Deaths that are the outcome of a SAE that occurs within 30 days from the last study treatment and are not due to disease recurrence.
- Deaths that occur at any time during the study and are considered by the investigator to be possibly or probably related to the study treatment.

Deaths that do not meet these criteria will not be reported as an SAE, but will be recorded on the CRF.

Version 4.0 Date: 08/21/2020

NCT02463799

The values for radium-223 in this protocol has been revised as per the US NIST standardization update (agreed on 17 Mar 2015)

## 7.6 Laboratory Test Result Abnormalities

The following laboratory abnormalities should be captured on the AE CRF or SAE Report Form as appropriate:

- Any clinically significant result that is not part of another reported clinical diagnosis.
- Any result that meets the definition of an SAE.
- Any result leading to study drug discontinuation or interruption.
- Any result that required therapeutic intervention or a change in subject management.

Laboratory abnormalities not meeting the above conditions will not be reported on the AE CRF or SAE report form.

## 8.0 STATISTICAL CONSIDERATIONS

### 8.1 General Considerations

This randomized phase 2 study is designed to test the null hypothesis of no difference in immune response to sipuleucel-T based on PA2024-stimulated T cell proliferation via tritiated-thymidine uptake between sipuleucel-T alone and sequential administration of radium-223

### 8.2 Sample Size Determination

The study is designed to test the null hypothesis of no difference in the stimulation index (SI) 6 weeks after the first vaccination with sipuleucel-T between sipuleucel-T alone and sequential administration of radium-223 and sipuleucel-T using PA2024-stimulated T cell proliferation via H-thymidine uptake as the assay. With 15 patients per treatment group, there is 80% power to detect a 3.6-fold increase in mean SI between the sequential radium-223 and sipuleucel-T and sipuleucel-T alone (data from OpenACT trial) at 6 weeks after the first sipuleucel-T infusion [18]. These power calculations are based on one-sided tests at the 0.05 level. The calculations assume that SI values are lognormally distributed with the same SD in each group, namely 1.4. The value of 1.4 comes from the P09-1 (OpenACT) trial.

To allow for drop-outs and subjects who may not receive 3 infusions of sipuleucel-T or 4 infusions of radium-223, 34 subjects will be enrolled.

### 8.3 Populations for Analyses

The immune response population will be defined as subjects who receive 3 infusions of sipuleucel-T and 2 infusions of radium-223. Analysis of immune response endpoints, including

Version 4.0 Date: 08/21/2020

NCT02463799

The values for radium-223 in this protocol has been revised as per the US NIST standardization update (agreed on 17 Mar 2015)

the primary endpoint, will be performed using this population. This population will also be used to perform supplementary analyses of non-immune response efficacy endpoints.

The safety population will include all subjects who receive at least 1 leukapheresis procedure or receive at least 1 dose of radium-223. All safety variables (e.g., AEs, laboratory data, and vital sign data) will be analyzed based on the safety population.

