## Study Population and Sample Size

Version 4.0 Date: 08/21/2020

NCT02463799

The values for radium-223 in this protocol has been revised as per the US NIST standardization update (agreed on 17 Mar 2015)

This study will enroll 30 evaluable patients with asymptomatic or minimally symptomatic mCRPC, 18 years of age or older. Up to 33 patients are estimated to be required to be enrolled to allow for drop-outs and subjects who may not receive 3 infusions of sipuleucel-T or 2 infusions of radium-223.

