## Statistical Considerations

The study is designed to test the null hypothesis of no difference in immune response to sipuleucel-T evaluated on the basis of PA2024-stimulated T cell proliferation via H-thymidine uptake between sipuleucel-T alone and sequential administration of radium-223.

For primary endpoint, PA2024-specific H-thymidine uptake was selected because it has demonstrated the highest signal to noise ratio and showed the strongest correlation with OS of all cellular and humoral assays evaluated in prior studies of sipuleucel-T.

With 15 subjects in each arm, we seek to detect a 3.6-fold difference between the arms with 80% power in mean SI of PA2024-specific H-thymidine uptake at week 6 after the first infusion of sipuleucel-T

The immune response population will consist of all subjects who receive 3 infusions of sipuleucel-T and at least 4 infusions of radium-223.

The intent-to-treat population is defined as all randomized subjects, regardless of whether they receive treatment. Analysis of non-immune response efficacy endpoints will be performed using this analysis population.

The safety population will include all subjects who undergo at least 1 leukapheresis procedure or receive at least 1 dose of radium-223.

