## **3.0 STUDY DESIGN**

This is a randomized study designed to assess the antigen-specific immune response of sipuleucel-T with or without radium-223.

Eligible subjects will be registered and randomly assigned in a 1:1 ratio to receive sipuleucel-T and radium-223 or sipuleucel-T alone;

Version 4.0 Date: 08/21/2020

NCT02463799

The values for radium-223 in this protocol has been revised as per the US NIST standardization update (agreed on 17 Mar 2015)

Arm 1: 6 infusions of radium-223 with 3 infusions of sipuleucel-T starting after second dose of radium-223

Arm 2: 3 infusions of sipuleucel-T alone

Subjects in both arms will undergo a standard 1.5 to 2.0 blood volume leukapheresis, followed approximately 3 days later by an IV infusion of sipuleucel-T. This process will occur a total of 3 times at approximately 2-week intervals. Subjects in Arm 1 will receive a total of 6 infusions of radium-223 at IV dose of 50 kBq/kg (55 kBq/kg after implementation of the NIST update) at 4-week interval.

All participants are allowed to receive the best supportive care which includes secondary hormonal manipulation (including flutamide, bicalutamide or nilutamide-but not abiraterone or enzalutamide) as required. No chemotherapy, external-beam radiation, or other radionuclides are allowed while on active treatment but are permitted after completion of active treatment. Glucocorticoid-containing treatments should be minimized to less than the equivalent dose of prednisone 10mg daily if feasible for the 3 months following sipuleucel-T therapy. All patients continue medical or surgical castration during treatment.

[figure not shown]
**Research visits** will be scheduled at screening, at each radium-223 infusion, prior to each leukapheresis (preleukapheresis visit), and week 32, 45 and 58 for Arm 1 (radium-223 and sipuleucel-T combination arm) and at screening, prior to each leukapheresis (preleukapheresis visit), and week 6, 10, 14, 26, 39, and 52 for Arm 2 (sipuleucel-T alone arm) for physical examinations, vital signs, ECOG performance status, adverse event (AE) monitoring, anticancer therapies, first opioid use for cancer-related pain, and laboratory tests. Serum PSA will be assessed at baseline, and week 16, 32, 45, and 58 for Arm 1 and at baseline, and week 10, 26, 39, and 52 for Arm 2. There is a  $\pm 7$  day window for each visit to accommodate holidays, vacations, etc.

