Abbreviations: AE = adverse event; A/P = abdomen/pelvis; CT = computed tomography; ECOG = Eastern Cooperative Oncology Group; F/U = follow up visit; Im = Immune assessment visit; JH = Johns Hopkins; MRI = magnetic resonance imaging; PAP = prostatic acid phosphatase; P/E = physical exam; PET = positron emission tomography; Sip = sipuleucel-T infusion visit; PS = performance status; PreL = preleukapheresis visit; PSA = prostatic specific antigen; Rad = radium-223 infusion visit; SAE = serious adverse event; Tx = treatment

- a. All screening procedures must occur within 28 calendar days prior to registration, with the exception of written informed consent, histological documentation of prostate cancer with Gleason grading, and imaging for confirmation of metastatic disease
- b. Radium-223 visits will occur 6 times at weeks 0, 4, 8, 12, 16, and 20
- c. Applies to all leukapheresis; pre-leukapheresis visits will occur  $\leq 5$  days prior to each leukapheresis. First sipuleucel-T infusion may occur any time between the second and third radium-223 infusion.
- d. At baseline, week 6, 10, 14, 26, 39, and 52 post-first sipuleucel-T infusion
- e. Follow-up visits will occur at every 3 months after week 58 visit for additional 1 year or until the subject's death
- f. Vital signs will be measured 1 to 30 minutes prior to, and at 30 minutes ( $\pm 10$  min) following each infusion
- g. Bone scan and CT or MRI abdomen/pelvis
- h. Per institution's standard procedure/at the investigator's discretion
- i. Only treatment-related events will be collected
- j. Baseline sample can be drawn at subject's "day one visit" (prior to dosing). See Appendix 1 for sample preparation instructions.
- k. Blood samples for antigen spread analysis will be collected at baseline (can be drawn at subject's "day one visit" (prior to dosing) , 1st pre-leukapheresis visit, and weeks 14 and 52 post-first sipuleucel-T infusion.
- l. PTT, PT/INR

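### The primary analysis set requires 2 radium-223 infusions in Section 8.3 but at least 4 in the synopsis, so which Arm 1 patients enter the primary t test is not fixed

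*Combined protocol and SAP*

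**What the plan says.** Section 8.3 states: "The immune response population will be defined as subjects who receive 3 infusions of sipuleucel-T and 2 infusions of radium-223". It then assigns the immune endpoints to this set; their analysis, including "the primary endpoint, will be performed using this population". The set also serves supplementary analyses of the other efficacy endpoints.

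The synopsis, under Statistical Considerations, defines the same named population differently: "The immune response population will consist of all subjects who receive 3 infusions of sipuleucel-T and at least 4 infusions of radium-223".

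Two further sentences set the enrolment allowance:

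- Synopsis, Study Population and Sample Size: "Up to 33 patients are estimated to be required to be enrolled to allow for drop-outs" and for "subjects who may not receive 3 infusions of sipuleucel-T or 2 infusions of radium-223".
- Section 8.2: the allowance is for patients who may miss 3 sipuleucel-T infusions or "4 infusions of radium-223, 34 subjects will be enrolled".

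All four are current text. On timing, footnote b of the Arm 1 schedule in Section 6.1 reads "Radium-223 visits will occur 6 times at weeks 0, 4, 8, 12, 16, and 20". Footnote c lets the first sipuleucel-T infusion fall anywhere between radium-223 doses 2 and 3. The control arm gets no radium-223 (Section 3.0): "Arm 2: 3 infusions of sipuleucel-T alone".

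**The concern.** The primary test in Section 8.6.3 is a t test on log SI with about 15 evaluable patients per arm. Two analysts who each follow the document could put different Arm 1 patients into it and report different primary results. If the rule is still open when SI results are available by arm, it could also be chosen with knowledge of what each choice gives.

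The two thresholds also differ in kind. Sipuleucel-T starts after radium-223 dose 2, so a 2-infusion rule removes almost nobody who began sipuleucel-T on plan. A 4-infusion rule is an additional filter on Arm 1 alone, and it can depend on treatment given after the endpoint was measured.

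**Working it through.** **1. The four statements side by side**

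| Place | Role | Radium-223 infusions | Enrolment |
|---|---|---|---|
| Synopsis, Statistical Considerations | defines the set | at least 4 | not stated |
| Section 8.3 | defines the set and assigns the primary endpoint | 2 | not stated |
| Synopsis, Study Population and Sample Size | drop-out allowance | 2 | up to 33 |
| Section 8.2 | drop-out allowance | 4 | 34 |

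Each number occurs once in the synopsis and once in the body.

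**2. Who is in dispute**

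Reading the 2 in Section 8.3 as a minimum, the disputed patients are those in Arm 1 with 3 sipuleucel-T infusions and exactly 2 or 3 radium-223 infusions. Patients who miss a sipuleucel-T infusion fail both rules. Section 5.9 stops all study treatment at disease progression, so a patient stopped for progression before the third sipuleucel-T infusion (week 10 in the Arm 1 table) also fails both. What remains is mainly patients who complete sipuleucel-T but stop radium-223 after dose 2 or 3. The documents give no count; that it is small is a judgement.

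**3. Timing of dose 4 against the primary sample** (radium-223 on schedule)

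- First sipuleucel-T: between dose 2 (week 4) and dose 3 (week 8).
- Primary sample: 6 weeks later, so 4 + 6 = week 10 to 8 + 6 = week 14.
- Dose 4: week 12. Section 5.7.3 allows a delay of up to four weeks, so it can move to 12 + 4 = week 16.
- Section 3.0 allows ±7 days for each visit.
- The Arm 1 table itself puts dose 4 and the first post-treatment immune sample in the same week, week 12.

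Dose 4 can therefore come before, with or after the sample.

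**4. The plan's power figure, and how far the threshold moves it**

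Inputs from Section 8.2: 15 per arm, 3.6-fold difference, SD 1.4 (taken as natural-log scale), one-sided 0.05.

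- ln 3.6 = 1.281. Standard error = 1.4 × √(2/15) = 0.511. Ratio = 2.506.
- Normal approximation: Φ(2.506 − 1.645) = 80.5%. By the noncentral t distribution: 78.8%. The stated 80% is reproduced and does not itself depend on the radium-223 threshold.
- Assume 17 randomised per arm (34 in total) and no loss in Arm 2. Noncentral-t power is then 83.3% at 17 vs 17, 82.2% at 16 vs 17 and 81.0% at 15 vs 17.

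**5. Can a bias be sized?**

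Suppose *k* of 17 Arm 1 patients are excluded, their mean log SI lies *d* SD below that of the rest, and there is no true effect. The comparison shifts by *k* × *d* × 1.4/17 on the log scale. Both *k* and *d* are assumptions. The table gives the apparent SI ratio, exp(shift), and the one-sided error.

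| Excluded | 1 SD above the rest | Same as the rest | 1 SD below the rest |
|---|---|---|---|
| 1 | 0.92, 3.5% | 1.00, 5.0% | 1.09, 6.9% |
| 2 | 0.85, 2.4% | 1.00, 5.0% | 1.18, 9.3% |

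The range lies on both sides of 5%, and nothing in the documents selects a cell.

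**The case against.** The best defence is that only two sentences define the set, and one of them has the better claim. Section 8.3 is the dedicated populations section, and it alone assigns the primary endpoint to the set. The sentences with 33 and 34 are enrolment allowances and define nothing. On this view the body governs, the synopsis is a slip, and the matter is clerical. In addition, few patients are likely to be affected, power hardly moves, and Sections 8.6.1 and 8.6.5 already report the size of the set and the number of radium-223 infusions received.

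Much of this stands. The allowances are not definitions, and 33 against 34 does not decide who enters the test. The power effect is minor, and exclusions would be partly visible afterwards. What does not stand is that the body settles it. No order of precedence is stated, and Section 8.2, also in the body, plans for losses against a threshold of 4. Reporting the size of the set after the fact does not say which set was meant.

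**Conclusion.** The contradiction is real, concerns the set for the primary test, and has to be resolved before the analysis. Its weight rests on the conflicting definition alone. The disputed group is probably small, though its size is unknown. Selection bias under the 4-infusion rule is possible, but neither its direction nor its size can be derived.

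Three stronger readings are tempting and are not supported:

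- A reader might infer that the 4-infusion rule inflates the type I error. That requires excluded patients to have systematically lower SI than the rest, and the documents give neither their number nor their SI. The error figures above are illustrations and carry no weight in this conclusion.
- A reader might infer that dose 4 precedes the sample only when sipuleucel-T starts after week 6. The visit windows and the shared week 12 rule out so sharp a statement. For example, with a start just after week 5, a sample drawn up to 7 days late can follow dose 4.
- Taken literally, neither definition limits the radium-223 condition to Arm 1, so both would empty Arm 2; and Section 8.3 omits a minimum, so exactly 2 might be meant. The design in Section 3.0 and the two-group comparison in Section 8.6.3 make clear that neither is intended. These are drafting slips to tidy in the same edit.

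**What to change.** Before any SI data are compared by arm, bring the two synopsis sentences and Sections 8.2 and 8.3 to one definition: 3 sipuleucel-T infusions in both arms and, in Arm 1 only, a stated minimum number of radium-223 infusions. The number is the sponsor's choice. Preferably count only infusions given before the week-6 sample, so that membership cannot depend on later treatment; the chosen number should then be checked against the Section 6.1 schedule, since dose 4 will not always have been given by then. Align the enrolment figure (33 or 34) in the same edit.

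Add a sensitivity analysis of all randomised patients with an evaluable week-6 SI, by assigned arm. Extend the tables in Sections 8.6.1 and 8.6.5 to show, by arm, how many were excluded or had no sample, and why.

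The cost is wording in four places, one extra analysis and one by-arm disposition table; no new data are needed. A limitation remains: any infusion-based set conditions on events after randomisation. The sensitivity analysis reduces this but does not remove it, because it still requires a sample. The change concerns the analysis set only and implies nothing about how much radium-223 patients should receive.
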